## 8.7 Qualitative Data Collection

Patient participants will be offered to participate in a qualitative study at the end of the cognitive training RCT. Participants will be invited to take part in either an interview or a focus group. Not all participants will be required to participate in the qualitative arm of the study.

### Semi-structured Interviews

At least 1 week after the completion of the CT program, participants will be invited to participate in semi-structured interviews to be held in the CHiASM research space, or the participant's home. All travel expenses will be paid to allow participants to attend the interviews. Participants will need to produce a receipt to claim expenses, and this will be outlined in the PIS.

A digital audio recorder will be used to record all the discussions continuously, and notes of non-verbal and paralinguistic clues will be made.

All digital recordings will be transcribed within 5-7 days of the interviews.

Semi-structured interviews are an iterative process, following the first couple of interviews the transcripts will be analysed and the themes and concepts emerging from this initial data will be further explored at the following interviews.

### Focus Group

At the end of the study period participants will be offered the option to take part in a focus group instead of participating in a semi-structured interview; the focus group will be held at the University of Leicester. All travel expenses will be paid to allow participants to attend the focus group. Participants will need to produce a receipt to claim expenses, and this will be outlined in the PIS.

The focus Group will be run by two named investigators, one of them will act as the moderator and the other will take written notes. A digital audio recorder will be used to record all the discussions. The interview schedule will be used to start the focus group discussions. The questions within the schedule will be the same as for the semi-structured interviews. The focus group will be taped continuously.

The digital recordings will be transcribed within 5-7 days of holding the focus group. The typed transcript will be read, and checked against the tape recordings for the completeness and accuracy, and any further comments will be added.

### Interview & Focus Group Schedule

An interview guide will be used in the semi-structured interviews and the focus group to provide a prompt for the topics that need to be discussed; these will be changed or modified as appropriate to the context of the conversation. The interview guide is a dynamic tool; it is not there to be prescriptive or ask closed response questions (36).

The interview guide will consist of questions on the following themes, specifically designed to explore the six predictors of health behaviours of the health belief model (risk susceptibility, risk severity, benefits to action, barriers to action, self-efficacy, and cues to action) (37) and to evaluate the cognitive training program and the experience of the participant and their carer:

1. What are the barriers to brain training in patients with dementia?
2. What are the facilitators (benefits) to brain training in patients with dementia?
3. Could brain training programs be adapted further to support the participation of patients with dementia?
4. Are there any additional benefits to brain training programs not measured by traditional methods as perceived by the patients and their carers?
5. To explore the lived experience of the patient and their carer and the impact brain training has on them and their life

#### 8.8 Definition of End of Trial

The end of trial is the date of the last visit of the final participant. The end of the qualitative study will be at the date of the last interview or focus group.

#### 8.9 Discontinuation/Withdrawal of Participants from Study Treatment

Each participant has the right to withdraw from the study at any time. In addition, the investigator may discontinue a participant from the study at any time if the investigator considers it necessary for any reason including:

Ineligibility (either arising during the study or retrospective having been overlooked at screening)

Significant protocol deviation

An adverse event which requires discontinuation of the study or results in inability to continue to comply with study procedures

Disease progression which requires discontinuation of the study or results in inability to continue to comply with study procedures  
Consent withdrawn  
Lost to follow up

If the participant is withdrawn due to an adverse event, the investigator will arrange for follow-up visits or telephone calls until the adverse event has resolved or stabilised. If a participant has been withdrawn from the study, they will not be required to attend any further assessments or follow-up. Participants who have withdrawn from the study will be included in the data analysis (intention to treat analysis) and will be consented to do so. In the healthy volunteer arm, as this is a feasibility study, withdrawn participants will not be replaced. The reason for withdrawal will be recorded in the CRF.

#### 8.10 Source Data

Source documents are original documents, data, and records from which participants' CRF data are obtained. These include, but are not limited to, hospital records (from which medical history and previous and concurrent medication may be summarised into the CRF), clinical and office charts, laboratory and pharmacy records, radiographs/scan reports, and correspondence, interview and focus group recordings and transcripts.

CRF entries will be considered source data if the CRF is the site of the original recording (e.g., there is no other written or electronic record of data). In this study the CRF will be used as the source document for; cognition (ACE-III), mood (GDS-15), function/ADLs (Lawton-IADL), quality of life (DEMQOL), handedness (Edinburgh Handedness Inventory), and assessments of neurovascular function (TCD), blood pressure, heart rate and ETCO2.

All documents will be stored safely in confidential conditions. On all study-specific documents, other than the signed consent, the participant will be referred to by the study participant number/code, not by name.

## **9. TREATMENT OF TRIAL PARTICIPANTS**

### **9.1 Description of Study Treatment**

Participants randomised to the intervention will complete an 8-12 week CT program. Participants will be required to complete five, 30 minute sessions per week for eight to twelve weeks. The CT program will be provided by Lumosity© as part of a collaboration through the Human Cognition Project. Lumosity© is a commercially available software, developed by a group of neuropsychologists, which has been used across several studies of brain training and disciplines (38-40). These studies have also been included in a number of systematic reviews and meta-analysis (6, 19). It is a multi-domain, online based cognitive training tool, which is relatively easy to use and administer. It has been designed to adapt to the individual's cognitive function in order to personalise the training program to their needs. Exercises will be selected with the support of Lumosity© to target the following cognitive domains; attention, memory, visuospatial, verbal fluency, and language.

### **9.2 Storage of Study Equipment or Related apparatus**

Study equipment is stored securely in the CHIASM laboratory and maintained annually by the medical physics department at the University Hospitals of Leicester NHS Trust.

### **9.3 Compliance with Study Treatment**

Compliance will be monitored through Lumosity© online software which will log and track the number of minutes and times per week a participant has spent training, to determine the training dose received by each participant. Participants will not be excluded based on non-adherence, as this is considered an integral component to the feasibility assessment.

## 10. SAFETY REPORTING

### 10.1 Definitions

#### 10.1.1 Adverse Event (AE)

An AE or adverse experience is:

Any untoward medical occurrence in a patient or clinical investigation participants, which does not necessarily have to have a causal relationship with this treatment.

An AE can therefore be any unfavourable and unintended sign (including an abnormal laboratory finding), symptom or disease temporally associated with the study, whether or not considered related to the study.

#### 10.1.2 Adverse Reaction (AR)

All untoward and unintended responses related to the study.

All cases judged by either the reporting medically qualified professional or the sponsor as having a reasonable suspected causal relationship to the study qualify as adverse reactions.

#### 10.1.3 Severe Adverse Events

To ensure no confusion or misunderstanding of the difference between the terms "serious" and "severe", which are not synonymous, the following note of clarification is provided:

The term "severe" is often used to describe the intensity (severity) of a specific event (as in mild, moderate, or severe myocardial infarction); the event itself, however, may be of relatively minor medical significance (such as severe headache). This is not the same as "serious," which is based on patient/event outcome or action criteria usually associated with events that pose a threat to a participant's life or functioning. Seriousness (not severity) serves as a guide for defining regulatory reporting obligations.

#### 10.1.4 Serious Adverse Event or Serious Adverse Reaction

A serious adverse event or reaction is any untoward medical occurrence that at any dose:

- Results in death,

- Is life-threatening,

NOTE: The term "life-threatening" in the definition of "serious" refers to an event in which the participant was at risk of death at the time of the event; it does not refer to an event which hypothetically might have caused death if it were more severe.

- Requires inpatient hospitalisation or prolongation of existing hospitalisation,
- Results in persistent or significant disability/incapacity, or
- Is a congenital anomaly/birth defect.
- Other important medical events\*

\*Other events that may not result in death, are not life threatening, or do not require hospitalisation, may be considered a serious adverse event when, based upon appropriate medical judgement, the event may jeopardise the patient and may require medical or surgical intervention to prevent one of the outcomes listed above.

#### 10.1.5 Expected Serious Adverse Events/Reactions

See Appendix D for a complete list of expected adverse events not subject to immediate reporting.

#### 10.1.6 Suspected Unexpected Serious Adverse Reactions

Not applicable for this type of study.

### 10.2 Reporting Procedures for All Adverse Events

All AEs occurring during the study observed by the investigator or reported by the participant, whether or not attributed to study, will be recorded on the CRF.

The following information will be recorded: description, date of onset and end date, severity, assessment of relatedness to study, other suspect device and action taken. Follow-up information should be provided as necessary.

AEs considered related to the study as judged by a medically qualified investigator or the sponsor will be followed until resolution or the event is considered stable. All related AEs that result in a participant's withdrawal from the study or are present at the end of the study, should be followed up until a satisfactory resolution occurs. It will be left to the investigator's clinical judgment whether or not an AE is of sufficient severity to require the participant's removal from the study. A participant may also

voluntarily withdraw from the study due to what he or she perceives as an intolerable AE.

The severity of events will be assessed on the following scale: 1 = mild, 2 = moderate, 3 = severe.

The relationship of AEs to the study will be assessed by a medically qualified investigator.

### 10.3 Reporting Procedures for Serious Adverse Events

All SAEs, except those expected ones defined in section 10.1.5 that do not require immediate reporting (see 10.1.5), must be reported to the Sponsor within one working day of discovery or notification of the event. The Sponsor will perform an initial check of the information and ensure that it is reviewed at the next R&D Management meeting. All SAE information must be recorded on an SAE form and sent to the Sponsor using the appropriate reporting form and the contact details on there. Additional information received for a case (follow-up or corrections to the original case) needs to be detailed on a new SAE form which must be sent to the Sponsor using the appropriate reporting form and the contact details on there.

The Sponsor will report all SUSARs to the Research Ethics Committee concerned. Fatal or life-threatening SUSARs must be reported within 7 days and all other SUSARs within 15 days. The CI will inform all investigators concerned of relevant information about SUSARs that could adversely affect the safety of participants.

In addition to the expedited reporting above, the CI shall submit once a year throughout the study or on request an Annual Report to the Ethics Committee which lists all SAEs / SUSARs that have occurred during the preceding 12 months.

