### **16.2 Data Safety Monitoring Committee (DSMC)**

As this is a non-pharmacological feasibility RCT, a DSMC is not required, but adverse events will be reviewed at TSC meetings.

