## 22. APPENDIX D: EXPECTED EVENTS NOT SUBJECT TO EXPEDITED REPORTING

Acute Coronary Syndromes	Malignancy
Agitation	Myocardial infarction
Angina	Nausea
Anorexia	Personality change
Anxiety	Peripheral Vascular Disease
Cognitive decline	Pressure sores
Constipation	Renal impairment
Delirium	Sedation
Depression	Seizure
Disease progression	Sexual dysfunction
Dysphagia	Sleep disturbance
Electrolyte disturbance	Stroke
Fall	Syncope
Fatigue	Transient ischemic attack
Fracture	Urinary retention/catheterisation
Gastrointestinal disturbance	Urinary tract infection
Hallucinations	Ulceration
Heart failure	Violent behaviour
Incontinence, faecal	Visual loss
Incontinence, urinary	Vomiting
Infections	Wandering
Institutionalisation / Admission to care home	Weakness
Intracerebral Haemorrhage	Weight loss
Loss of ability to function or care for self

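### A serious event that is on the Appendix D list and is related to the study has no reporting deadline, and sections 10.1.6 and 10.3 contradict each other on SUSARs

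*Combined protocol and SAP*

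**What the plan says.** All references are to the combined protocol and SAP.

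- **Section 10.3** says that serious adverse events "must be reported to the Sponsor within one working day of discovery or notification of the event". The rule opens with its exception: "All SAEs, except those expected ones defined in section 10.1.5 that do not require immediate reporting".
- **Section 10.1.5**, whose heading covers both serious adverse events and reactions, has one sentence of content: "See Appendix D for a complete list of expected adverse events not subject to immediate reporting".
- **Appendix D** is a two-column list of event names. One entry is "Intracerebral Haemorrhage"; others are stroke, myocardial infarction, seizure, fall, fracture and malignancy.
- **Section 10.1.6**, which should define SUSARs, says only "Not applicable for this type of study".
- **Section 10.3** then says "The Sponsor will report all SUSARs to the Research Ethics Committee concerned", with 7 days for fatal or life-threatening cases and 15 days for the rest.
- **Section 10.2** has every adverse event recorded on the CRF, and a medically qualified investigator assesses its relationship to the study.
- **Section 16.2** says that "a DSMC is not required, but adverse events will be reviewed at TSC meetings". Section 16.1 sets those meetings at six-monthly intervals.

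**The concern.** An exemption from prompt reporting is normally meant for events that are common in the population and have nothing to do with the study. Here it depends on the name of the event alone. A seizure or a fall that the investigator attributes to a study procedure would fall under the exemption just as an unrelated one would.

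The SUSAR text looks like the safety net for related serious events, but it does not catch this case, because a listed event is by definition expected. The net itself is also uncertain, since one section sets it aside and another makes it compulsory.

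What is at stake is how soon the Sponsor learns of a serious event that the study may have caused. Some participants in this trial will lack capacity to consent (sections 8.3 and 14.1), and there is no DSMC.

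**Working it through.** No sample-size or error-rate figure is involved. The check is a count, followed by a reading of the reporting sections side by side.

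**Size of the list.** Appendix D has 24 terms in the left column and 23 in the right: 24 + 23 = 47, all distinct. A search of the terms for words on relatedness, death or fatality finds none.

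**Conditions on the exemption.**

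1. 10.3 exempts the expected events defined in 10.1.5 and adds no condition.
2. 10.1.5 points to the whole of Appendix D and adds no condition on cause or outcome.
3. 10.1.2 defines an adverse reaction as a response related to the study. The word reactions in the heading of 10.1.5 therefore brings related events within the section.
4. 10.1.4 makes death a criterion of seriousness, but no section takes a fatal listed event out of the exemption.

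**Routes by type of related serious event.**

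| Related serious event | To the Sponsor | Onward to the ethics committee |
|---|---|---|
| On the Appendix D list | SAE form, no stated time limit | Not a SUSAR, because expected; annual report only |
| Not on the list | One working day | 7 or 15 days under 10.3, but 10.1.6 says not applicable; annual report in any case |

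The first row has no entry with a short deadline. That remains so however the conflict between 10.1.6 and 10.3 is resolved, because an expected event is not a SUSAR on either reading. The second row keeps its one-day step, and only its onward step depends on resolving the conflict.

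**Use of the relatedness judgement.** Under 10.2 it decides which events are followed until they resolve or stabilise. It plays no part in the exemption in 10.3, although the information is already collected.

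**The case against.** The best defence has four parts.

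**Listed events are still reported.** This is correct. 10.3 also says that all SAE information goes to the Sponsor on a form, and that sentence contains no exemption. Listed events are on the CRF, open to TSC review and included in the annual report, which can also be requested. What is missing is a time limit.

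**Independent review is no slower.** A reader might infer that the exemption moves independent review from one working day to six months (TSC) or twelve months (annual report). The documents do not support this. One working day is the time to notify the Sponsor, who then makes an initial check and takes the event to its next R&D Management meeting. Non-exempt events reach the TSC and the annual report on the same cycle as exempt ones.

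**The inclusion of related events is an inference.** It rests partly on one word in a heading; the sentence beneath it and the title of Appendix D speak only of events. This is fair as far as it goes. But 10.3 says nothing to exclude related events, so the plain wording covers them. Likewise, 10.1.6 may mean only that no SUSARs are anticipated, but it does not say so and it gives no definition.

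**The risk is low.** The background section reports no adverse effects of cognitive training, and section 14.1 describes the measurement procedures as well tolerated. That suggests that related serious events will be few. It also means that prompt reporting of them would cost little.

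**Conclusion.** The point holds in a limited form. On the wording of 10.3, 10.1.5 and Appendix D, a related serious event under any of 47 terms has no reporting route with a deadline. Separately, 10.1.6 and 10.3 contradict each other on SUSARs, which leaves the 7- and 15-day ethics route for unlisted related events uncertain.

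The size is the loss of one deadline, the one working day to the Sponsor, for related listed events. The documents give no figure for how many such events to expect, so no rate can be attached.

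Two wider readings go too far. Not every related serious event lacks a fast route, since unlisted ones keep the one-day rule. And the documents give no data on admissions, so the share of serious events that the list would cover cannot be stated.

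The conclusion assumes that the exemption means what it says, and that no Sponsor procedure outside these documents adds a relatedness condition. Section 14.2 refers to Sponsor SOPs, which are not part of the material reviewed.

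**What to change.** 1. **In 10.3**, limit the exemption to Appendix D events that the medically qualified investigator has judged unrelated to the study under 10.2. Related listed events then follow the existing one-working-day rule. With that wording, an event not yet assessed is not exempt.
2. **Reconcile 10.1.6 with 10.3.** Either define the related and unexpected serious events to which the 7- and 15-day text applies, or remove that text.

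Appendix D can stay as a single list; it need not be divided by population. The change takes a few sentences in section 10. It needs no new data, because relatedness is already recorded and an SAE form is already required. The costs are that a few SAE reports must be sent sooner, and that relatedness must be judged promptly for a listed event to be exempt; 10.2 sets no time for that judgement at present.

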## 11. STATISTICS

### 11.1 Description of Statistical Methods

All data will be tested for normality prior to statistical testing using Shapiro-Wilks or visual inspection of histograms. Where data are found to be non-parametric, data will be appropriately transformed prior to statistical testing, and parametric tests then applied. Data will be recorded in Microsoft Excel. Statistical analyses will be performed using the latest version of SPSS for Windows, and graphs will be produced using the latest version of GraphPad Prism for Windows.

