#### Feasibility and Baseline Demographics

Data will be reported as mean (standard deviation) for continuous variables, and number (percentage) for nominal data. Differences between the intervention and control groups will be analysed within population group (HC/AzD/MCI) using Chi-Square for nominal data, and independent t-testing for continuous data. Any differences between population groups will also be reported.

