#### Outcome Data

The difference for each participant between baseline and follow-up assessment for each of the continuous outcome measures described in Section 6.2 (secondary outcome measures) will be reported along with the overall mean difference. To assess the impact of the intervention and population group on each of these differences, a two-way ANOVA will be carried out. The interaction between population group and treatment group will also be included to assess if the difference between the treatment groups is different between the population groups.

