#### Power calculation

The results from this study will be used to inform a power calculation to determine the sample size for a larger trial investigating the outcome measures described in Section 6.2. Specific statistical support will be sought within the Department of Cardiovascular Sciences to carry out this power calculation using the outcome data from this study.

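### The transform-then-parametric rule in section 11.1 does not specify residuals, has no fallback for heavily tied change scores, and can move the ANOVA and its interaction off the scale on which results are reported

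*Combined protocol and SAP*

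**What the plan says.** The opening paragraph of section 11.1 sets one rule for every analysis: "All data will be tested for normality prior to statistical testing using Shapiro-Wilks or visual inspection of histograms". The consequence of failing follows: "Where data are found to be non-parametric, data will be appropriately transformed prior to statistical testing, and parametric tests then applied". No transformation is named. Nothing is said about residuals, back-transformation, or what happens if the transformed data still fail.

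Under Outcome Data in the same section, the analysed and reported variable is "The difference for each participant between baseline and follow-up assessment for each of the continuous outcome measures described in Section 6.2", which "will be reported along with the overall mean difference". The test is then given: "To assess the impact of the intervention and population group on each of these differences, a two-way ANOVA will be carried out". A population-by-treatment interaction is part of that model. Section 6.2 lists the secondary outcomes: ACE-III, Lawton IADL, GDS-15, DEMQOL and the task-related CBFv response.

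Under Power calculation, a later and larger trial is to be sized by a "power calculation using the outcome data from this study". The commitment to summary statistics, "Data will be reported as mean (standard deviation) for continuous variables, and number (percentage) for nominal data", stands under Feasibility and Baseline Demographics and not under Outcome Data.

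**The concern.** There are three difficulties.

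1. **No end point.** Changes on short integer scales can be exactly zero for many participants. A transformation that maps equal values to equal values leaves such a spike in place. The rule still calls for a parametric test on data that failed its own condition.
2. **Unclear target.** The ANOVA assumption concerns residuals within the population-by-arm cells. Read as a check on pooled data, the rule can flag outcomes whose errors are perfectly normal, simply because the sub-groups change by different amounts.
3. **Scale.** Whether the treatment effect differs between populations depends on the measurement scale. A transformation chosen after seeing the data can alter the answer to the interaction question, and it puts the ANOVA estimate and residual SD in units other than scale points.

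At stake are the interpretation of the secondary analyses and the form of the figures handed to the next trial's sample size calculation.

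**Working it through.** The plan gives no effect size, SD or power to reproduce, so the check is by reasoning and simulation.

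**Inputs from the document.** Sub-groups of 20; total 60 in three sub-groups (section 11.2) or 80 in four (Synopsis); significance level 0.05 (section 11.3); two-way ANOVA with interaction on change scores (section 11.1).

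**Assumed inputs.** 1:1 allocation, so 10 per cell; integer changes from -3 to +2 with 30-80% exact zeros; the effect sizes and spreads stated below. The documents give no distribution of change for any outcome.

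**Step 1: ties.** If x_i = x_j, then g(x_i) = g(x_j) for any function g. With 50% zeros, 0.5 × 60 = 30 or 0.5 × 80 = 40 participants share one value before and after transformation. Shapiro-Wilk at 0.05 was applied to untransformed data and after shifted log, shifted square root, asinh, cube root and Yeo-Johnson (1,000 data sets per setting):

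| n | Share of zeros | Data sets in which any version passed |
|---|---|---|
| 60 or 80 | 30-80% | 0% |
| 20 | 30% | 67% |
| 20 | 50% | 27% |
| 20 | 60% | 9% |
| 20 | 70% | 0.8% |
| 20 | 80% | 0.2% |

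The rule therefore has no workable end point at the pooled sizes. Within a single sub-group of 20 the outcome depends on the share of zeros.

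**Step 2: negative values without ties.** For continuous, skewed changes that include negatives, Shapiro-Wilk rejected 99-100% untransformed. After Yeo-Johnson it rejected 11% (n=60) and 18% (n=80). Negative values alone do not defeat the rule.

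**Step 3: pooled data or residuals.** Errors were exactly normal and one sub-group's mean change was shifted:

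| Shift | Pooled, 3 groups (n=60) | Pooled, 4 groups (n=80) | Residuals |
|---|---|---|---|
| 1 SD | 5% | 5% | 5-6% |
| 2 SD | 12% | 22% | 5% |
| 3 SD | 60% | 83% | 4-5% |

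Pooling causes wrong flags only when mean changes differ by about 2 SD or more.

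**Step 4: interaction.** Let a sub-group's mean, after shifting to positive values, be m, and let the treatment effect be d in every sub-group. On the original scale the effect is d everywhere, so there is no interaction. On the log scale it is approximately log(m + d) - log(m) = log(1 + d/m), which varies with m. In simulation with right-skewed gamma errors, 10 per cell and a nominal 5% test:

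| Spread of sub-group mean change | Treatment effect | Original scale | Shifted log |
|---|---|---|---|
| 2-3 SD | 1 SD | about 5% | about 15-24% |
| 2-3 SD | 0.5 SD | about 5% | 8-11% |
| none | either | about 5% | no inflation |

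**Step 5: is transformation needed?** With 50-80% zeros and 10 per cell, the untransformed two-way ANOVA had type I error of 4.6-5.2% for treatment and 4.2-5.4% for interaction. In these settings there was no error-rate problem for a transformation to solve.

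**Step 6: choice of interval.** At 10 per arm, percentile-bootstrap intervals for the between-arm difference were about 12% narrower than t intervals and covered 91-92%, against 95-96% for t. At 40 per arm they were still 3% narrower.

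**The case against.** It can fairly be said that the rule is a common convention, leaves sensible discretion and does little harm. Several stronger criticisms that a reader might infer are indeed not supported.

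- **That the rule cannot work because changes can be negative.** If the mean change is zero and the distribution is symmetric, half the values are at or below zero and a plain log is undefined there. But the plan never proposes a log, and Step 2 shows that other transformations accept negatives.
- **That raw pooled scores are tested.** The text speaks of all data and leaves raw or residual open. It also allows inspection of histograms, so Shapiro-Wilk rejection rates do not by themselves decide what an analyst would do.
- **That pooling usually triggers false flags.** With assumed ACE-III levels of 94, 84, 66 and 86 and SD 6, pooled data fail in 72% of samples. The ANOVA uses differences, however, in which stable gaps between populations cancel. For changes in four sub-groups the figure is about 5-23% at shifts of 0.5-2 SD. The baseline t-tests, which do use levels, are run within population.
- **That the original scale is lost.** Individual differences and the overall mean difference are reported separately from the ANOVA, transformation is prescribed for testing, and SDs can be computed from the untransformed data.
- **That scores will be mostly zero.** The documents do not say so.

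What remains after these concessions is the missing fallback, the unspecified target of the check, the change of scale for the ANOVA and interaction, and the absence of a commitment to arm-level SDs or intervals. Discretion does not help with ties, because no choice of one-to-one transformation removes them.

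**Conclusion.** The point holds in this limited form. For heavily tied change scores the rule cannot reach its intended end at n=60 or 80, under the assumed zero shares of 30-80%. For any outcome that is transformed, the treatment effect and the interaction are tested on a different scale from the reported differences. Inflation of the interaction test to about 15-24% requires a shifted log, sub-group mean changes spread over 2-3 SD and a 1-SD treatment effect. It shrinks to 8-11% with a 0.5-SD effect and vanishes if mean changes are equal. The figures for the later power calculation can be recovered from the data, but the plan does not commit to reporting them by arm.

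Severity is minor to moderate. The primary endpoints are feasibility measures and are untouched, and no conclusion about efficacy should rest on these secondary tests.

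**What to change.** Replace the test-then-transform rule in section 11.1 with the following:

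1. Fit the planned two-way model to change on its original scale for every secondary outcome.
2. Check the model residuals graphically, with no formal normality test acting as a gate.
3. Report the mean and SD of change by arm, and the between-arm difference with a t-based or small-sample heteroscedasticity-robust 95% CI. Do not use percentile-bootstrap intervals with about 10 per arm, because they are too narrow.
4. Where residuals are clearly non-normal, add a permutation p-value for the arm effect, permuting arm within population, as a sensitivity analysis. This tests no effect in any population; it is not a test of the interaction.
5. Under Power calculation, state that the arm-level SDs of change and their uncertainty are the inputs to be carried forward.

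The cost is a few sentences of SAP text, a little extra analysis and possibly slightly wider intervals. No data collection or trial procedure changes.
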